3.2.1 Collection of written text for natural language analysis

The Natural Language Analysis (NLA) component of FrailSafe aims to detect signs of cognitive deficiencies in written text. Especially for determining a person's mental state, a textual input is more significant than a speech utterance, since the latter can be distorted by many unrelated factors that can produce false positives when searching for mental peculiarities. Given a textual input, then spelling errors, syntactic discrepancies, and semantic misinterpretation are just a few indicators that when combined with a personalized user model that stores information about the educational level of an individual or its previous linguistic state, can allow the tool to trigger alerts. These alerts could be distributed

appropriately (e.g., to the writer, to his/her relatives, to his/her doctor, etc). Over time the person's use of the language evolves, but since this process is very slow, sudden out-of-the-norm inputs will also be able to trigger alerts.

In the beginning of each participant's recruitment, samples of text written by her/him will be collected, preferably in electronic typed (UTF-8) format. If this is not possible, other modes of written text (e.g. handwritten text, dictated text to one of the personnel's member, etc) will be collected and converted to typed UTF-8 format, each with a tag mentioning the mode of original input. All collected texts will be registered to the database for analysis after the permission of the individual. The security and confidentiality of personal data will be reassured by the structure of the database (see section 5: Ethics and safety).

In practice, we ask the participant to show us a sample of their old writings (preferably emails, Word documents, etc). The second step is collecting text from the present moment. In order to stimulate the participant's inspiration, possible subjects for writing are provided in the questionnaire, but this is by no means restrictive to the person's choice of what to write. Finally, a picture (annex 14) is provided in order for the participant to describe what is illustrated there. The written text collection task is given to the participant to prepare at their home, except in case where they are unable to write themselves, so it will be dictated during either the clinical evaluation or the home visit. If the person is capable of preparing the texts him/herself, an instructions' sheet is delivered to them (annex 15) and it is collected filled in during the nurse's home visit. Table 15 describes the instructions to the clinician for written text collection.

Table 15. Data collection of written text (first time)

Step 1	Ask for previous text (e-mails, letters, etc.).
	Preferably typed (else handwritten)
	Either we have already asked the participant to bring with him some old text when (s)he comes to the clinical evaluation appointment, OR we ask him/her to prepare something to show to the person that is going to realize the home visit, OR we ask him/her to send them via e-mail if they have the ability to do that.
	If electronic typed text is not available, then photos of available texts should be taken, after the consent of the person, paying also attention in the "sensitive" character of some types of documents.
Step 2	Ask to think of a major life event and to write it down.
	If possible typed (by preference), otherwise handwritten. If not possible dictated.

Ask to think of a recent, everyday life routine, e.g. write what he/she did in the previous day (this is a question that will be repeated in future sessions as well, since it produces valuable differential data for each individual).

Ask to think a major enjoyable life event, although unpleasant events should not be dismissed.

For instance:

- Wedding
- Child's birth.
- Children's achievements
- Enjoyable travel experience.
- Professional achievements.
- Last time you felt excitement about a forthcoming event.

Step 3Show attached picture and ask to describe it in written text (Annex 14)If possible typed (by preference), otherwise handwritten. If not possible
dictated.

After the first written text collection, new samples of written text arecollected in each clinical visit, according to the second step's model:

Table 16. Data collection of written text (in every clinical assessment after the first)

Ask to think of a major life event and ask to write it down.

If possible typed (by preference), otherwise handwritten. If not possible dictated.

Ask to think of a recent, everyday life routine, e.g. write what he/she did in the previous day.

Ask to think a major enjoyable life event, although unpleasant events should not be dismissed. For instance:

- Wedding
- Child's birth.
- Children's achievements
- Enjoyable travel experience.
- Professional achievements.
- Last time you felt excitement about a forthcoming event.

Annex 14 presents the picture that the participants is asked to describe, while annex 15 contains the sheet that is given to those who are capable to fill in the written text themselves at their homes.

For the collection and the management of the data related to written text, the physician or nurse will use one of the mobile devices given to their use by the study and a special application for scanning, storing and sending documents centrally to the database system.

Natural language analysis will employ both statistical and informational based methods of text mining / machine learning in order to reveal information concerning the individual's mental state from their writings. Specifically, the process of text writing will be treated as a Hidden-Markov Process, where the person's mental state evolves over time but we do not have direct data on this evolution, but only indirect evidence (the written text) that can reveal the (hidden) mental state. Therefore, each piece of text will undergo a series of tests/transformations, i.e:

- tf-idf statistical filtering
- bag-of-words transformation
- cosine-distance cross-comparison with other samples
- headword/keyword sentiment analysis
- entropy estimation
- redundancy estimation compared to other samples
- syntactic parse quality test

The methods that will be employed will be specifically trimmed in order to cope with small size texts as are the samples that we are expecting to collect. The evolution over time of the above characteristics, as well as the cross-comparison with the metrics of other individuals in the general population will enable us to automatically detect any irregularities in the written text samples.

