- 10. Daily phone calls during the instauration of the FrailSafe system to catch up with the experience of the use of the material and any problems that may have arisen
- 11. Short satisfaction interview in the day of FrailSafe system retrieval
- 12. Telephone Follow-up after the retrieval of the FrailSafe in a 3 months' basis (table 17). (M9-M24)
- 13. Second clinical evaluation (M27) (tables 5-14)
- 14. Data collection of written text after the first time (table 16) (M27). The participant will either be helped to provide text by dictation or be asked to prepare it him/herself in his/her home and deliver it to us in the next appointment
- 15. Second FrailSafe system instauration (M27)
 - [Only for Patras]: blood sampling
 - Fill in the evaluation form regarding the participant's housing (table 18)
 - Collect any questionnaires filled in by the participant since the last visit (written texts)

- Complete any missing information of the clinical evaluation (i.e. scanning of a forgotten prescription, scanning of an older written text provided by the participant, write down dictated text)
- Administration of follow up questionnaire (table 17)
- Installation of the currently available FrailSafe system and reminding of the use, the purposes and the technical issues of the FrailSafe material (Session 3.8). Verification of its correct function
- Provide contact details and instructions in case of any help needed
- Set the next appointment to retrieve the FrailSafe material (5th day)
- 16. Maintenance of the FrailSafe system at home during 3-5 days
- 17. Daily phone calls during the instauration of the FrailSafe system to catch up with the experience of the use of the material
- 18. Telephone Follow-up after the second retrieval of the FrailSafe (M30) (table 17)
- 19. Last clinical evaluation (M33) (tables 5-14)
- 20. Data collection of written text after the first time (table 16) (M33). The participant will either be helped to provide text by dictation or (s)he will write it down during the clinical assessment appointment
- 21. Last telephone follow up M36
- 22. Study's completion verification (table 20). Normally at the end (M36), but could be in anytime in case of premature withdrawal.

Did the patient complete the study as predicted?	1. Yes 2. No

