Annex 14- The picture provided for written description

Annex 15- Data collection of written text (self-administration): Form given to the participant to fill in at home in case (s)he is capable of doing so

Dear Mr/Mrs

We are very interested in your writings and the way it can alter in time. In order to perform a text analysis we need you to provide us with some written texts, older and current.

[figure not shown]
- 1) Please prepare something **that you have written some time ago** to show to our colleague who will visit you at home
- 2) Please think, a major event of your life or anything else you like. For example you could **describe an enjoyable life** event like:

A wedding Your child's or grandchild's birth Some of your personal or your children's achievements An enjoyable travel experience Professional achievements Last time you felt excitement about a forthcoming event.

Or even an unpleasant even if you like.

Now please type in a text your thoughts. If it is not possible to type, then write it down by hand. If for any reason you are unable to write, then please, dictate it to our colleague who will visit you at home

3) Please, now type in **what you see in the picture**. If it is not possible to type, then write it down by hand. If for any reason you are unable to write, then please, dictate it to our colleague who will visit you at home

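### The previous-day text is the task chosen for repetition, but the home sheet used at entry omits it, so home writers have no baseline on it

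*Protocol*

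**What the plan says.** Section 3.2.1 of the protocol treats writing as indirect evidence of a hidden mental state and relies on change within a person: "The evolution over time of the above characteristics, as well as the cross-comparison with the metrics of other individuals" is to reveal irregularities.

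The first collection (Table 15) has three steps: an old text, a set of writing prompts, and a description of the Annex 14 picture. Of the previous-day prompt in step 2 it says: "this is a question that will be repeated in future sessions as well, since it produces valuable differential data for each individual". Later samples are collected "in each clinical visit, according to the second step's model", that is, by step 2 only. Table 16 repeats the life-event and enjoyable-event prompts and again asks the participant to "write what he/she did in the previous day".

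The first writing task "is given to the participant to prepare at their home", unless the person cannot write and dictates instead. Those who can write receive the Annex 15 sheet. It has three items: something written some time ago, a text introduced by "Please think, a major event of your life or anything else you like", and the picture.

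For the last collection in groups A, B, Ci, Cii and D, the step lists of Section 4 say: "The participant will either be helped to provide text by dictation or (s)he will write it down during the clinical assessment appointment". Section 3.2.1 also provides a tag for the original input mode (such as typed, handwritten or dictated). It describes no tag for the prompt or for where the text was written.

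**The concern.** The previous-day account is the only writing prompt that the protocol marks for repetition, and the reason given is that it yields differences within a person. A difference needs two texts, and the default form for the first collection does not request one of them. The omission lies in the data-collection form, so no later analysis plan can recover the missing text.

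Home writers do share a life-event text between entry and follow-up, but its topic is left to the participant. Several of the listed features (bag-of-words, tf-idf, cosine distance, sentiment) depend directly on topic, so a difference between two free-topic texts is hard to interpret. The move from home to clinic at the last collection adds a second difference that the described tags would not identify.

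Natural language analysis appears in two rows of Table 22 and so contributes to the Clinical Frailty Index. Section 5.2.3 lists the difference between Clinical Frailty Indices as a measurable change.

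**Working it through.** The protocol gives no figure to reproduce here. The check sets the forms side by side and counts texts.

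**Prompts by form**

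| Prompt | Table 15 (first) | Annex 15 (home sheet) | Table 16 (later) |
|---|---|---|---|
| Old text | yes | yes | no |
| Life event | yes | yes, or any topic | yes |
| Previous day | yes, marked for repetition | **no** | yes |
| Enjoyable event | yes | as an example of a life event | yes |
| Picture | yes | yes | no |

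The previous-day prompt is in both clinician tables and missing only from the home sheet.

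**Previous-day texts available for a home writer**, using the Section 4 months, with Annex 15 at entry and the Table 16 prompts at every later evaluation:

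| Group | Collections | Previous-day texts | Longest available interval | Interval with an entry text |
|---|---|---|---|---|
| A | entry, M27, M33 | 2 of 3 | 33 − 27 = 6 months | up to 33 − 6 = 27 months |
| B | entry (M10), M16, M22, M35 | 3 of 4 | 35 − 16 = 19 months | 35 − 10 = 25 months |
| C | entry (M31), M36 | 1 of 2 | none | 36 − 31 = 5 months |
| D | entry (M31), M36 | 1 of 2 if the home sheet is used | none in that case | 5 months |

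**Setting.** Texts at M27 in A and at M16 and M22 in B may again be prepared at home. The last text (M33 in A, M35 in B, M36 in C and D) is dictated or written in clinic. For a participant who wrote at home each time this was allowed, the only previous-day pair in A (M27, M33) crosses the change of setting. B has one home-to-home pair, M16 to M22, spanning 22 − 16 = 6 months.

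**Dependence on how the sheet is used.** Annex 15 is not labelled as first-time only, and Section 3.2.1 mentions it again after Table 16. If it were reused at the interim home collections, the previous-day text would be missing there as well. A would then have it only at M33 and B only at M35.

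**Who can still be helped.** A and B make up 3 × (80 + 40) = 360 of the 510 participants, and their entry collections were planned before this revision, which is written at M23. C and D make up 3 × (25 + 25) = 150 and start at M31.

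**The case against.** Much can be said for the plan as it stands, and most of it limits the point.

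- A reader might infer that the texts cannot support any within-person change. That goes too far. Life-event prompts are common to Table 15, Annex 15 and Table 16. A and B can have repeated previous-day texts during follow-up. Participants who dictate under Table 15 receive the prompt at entry.
- A reader might also infer that leaving the picture out of follow-up is an error. The protocol states the choice to repeat step 2 only, and a repeated picture brings a familiarity effect. Annex 15 could even bring the picture back if it is reused.
- It is tempting to say that every home writer changes setting. For group D this is not shown: Section 3.4 gives D no home visits, and Section 4.5 lists no first text collection. The documents state no time limit in either setting, so a timed-versus-untimed contrast has no basis.
- The nurse may help the participant write the text (Annex 19), and Table 15 remains the clinician's instruction. The missing prompt could therefore be supplied in practice, but no step tells anyone to add it for a person who writes from the sheet.
- In the comparison of C with D, the last text has the same setting options in both arms. The change of setting therefore bears mainly on within-person change.
- The stakes are modest. Language analysis is neither a hard nor a proxy outcome, and it fills 2 of the 46 rows listed in Table 22.

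None of this supplies an entry previous-day text for a participant who follows Annex 15.

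**Conclusion.** The protocol contradicts itself. Table 15 marks the previous-day text for repetition and Table 16 repeats it, yet the default home sheet leaves it out. For home writers this removes the entry value of the designated measure. In C, and in D if the sheet is used there, it removes any change on that measure. In A and B it shortens the usable interval to 6 and 19 months, provided that the interim texts used the Table 16 prompts. The move from home to clinic is a second, smaller weakness, because setting is not recorded.

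The conclusion assumes that home writers follow Annex 15 as printed. Their number is not given; the protocol makes home writing the default for anyone able to write. A reader might infer that a change of task or setting will be reported as a change in mental state. The documents do not establish that: they show that it could not be ruled out from the tags described. The correction is worth making before C and D begin. It does not call the whole language component into question.

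**What to change.** 1. Add the previous-day prompt to Annex 15 before groups C and D start at M31.
2. Record the prompt and the setting (home or clinic) with every text, next to the existing mode tag.
3. Compute within-person change only between texts of the same prompt and input mode. For A and B home writers without an entry previous-day text, take the first follow-up one as the reference.
4. Where a matched setting is wanted in C and D, have the entry previous-day text written during the first clinical appointment, as the last one is. Sending the last text home instead does not fit the schedule: no later visit exists at which to return it in B (M35) or in C and D (M36), and A has only a telephone call after M33.

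Repeating the picture at follow-up is optional.

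The cost is one added prompt, two recorded fields and a few extra minutes per participant. A and B home writers keep a shorter change interval, because their entry previous-day text cannot be recovered.

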3.2.2 Self-administered questionnaires

Since the majority of the now-aging European population is technologically literate, many people may use social media like Facebook, Twitter and other publicly-available fora and chat-rooms to communicate with friends and relatives. Even short messages posted there can provide valuable information concerning the writer's mental and emotional state, not to mention the new means of communication aspects that they provide. In order to collect information regarding social media use the Social Media Questionnaire are employed (annex 16).

Moreover, to identify personality traits we employ the most widely known model of personality trait qualification, the Big Five questionnaire (annex 17). According to Big Five, the human personality is described as a vector of five values of traits. The combination of Big Five personality dimensions explains the dynamics of a personality. For example, a person

may be very talkative (high Extraversion), not very tolerant and sensitive (low Agreeableness), systematic and punctual (high Conscientiousness), easily anxious (high Neuroticism) and extremely curious (high Openness). This personality characterization will be automatically extracted and taken into account in the frailty metric. In addition it will help in improving the services proposed by our approach to the individual according to his/her personality and current emotional state.

Similarly as the written text collection, these two questionnaires are delivered to the participants in order to fill them up themselves in the beginning of their recruitment, typically, during the first clinical evaluation visit. After completion of the questionnaires, the sheets are handed back by the participant to a study's member during their next programmed appointment, typically to the nurse during the FrailSafe system home visit. In opposition to the written text collection, which will be taking place during each clinical evaluation session all over the duration of the study, the social media and big five questionnaires are answered only once, at the phase of the subject's recruitment.

3.3 The (phone) follow up questionnaire

After the first evaluation triplet takes place (clinical assessment appointment, FrailSafe system home visit and blood sampling), the follow up by a short battery of questions (table 17) monitors the occurrence of adverse events like falls, fractures, hospitalisations and/or death. This follow up, which is programmed for every 3 months' time, will be done either by telephone or incorporated in a coinciding FrailSafe system home visit or clinical assessment appointment.

These outcomes, which represent main complications of frailty, triggering factors for shifting from one frailty level to another and potential prevention goals, are also defined as the study's hard outcomes (section 5.1).

Falls	Did any fall occur?	Yes/no
	Number of falls	
	Date of the event	
Fractures	Did any fracture occur?	Yes/no

	Date of the event	dd/mm/yyyy
	Anatomic location	Click all that apply: o upper limps o hip-pelvis o vertebral o other o multiple factures "I don't know" option also provided
Hospitalizations	Did any hospitalization occur?	Yes/ No
	Date	dd/mm/yyyy
	Length of hospital stay (in days)	+option of "still hospitalized" provided
	Outcome	 totally cured amelioration stability worsening of general health state death institutionalization still hospitalised
Conditions of hospital recours	 programmed hospitalization visit to the emergency care room by release without hospitalisation urgent hospitalization 	
Death	Did death occur?	Yes/no
	Cause	Open field for the cause of death +option of "I don't know also provided"
	Date	dd/mm/yyyy

In a six months' basis, this questionnaire will be completed with the ADL/IADL questionnaires (Annexes 6 and 7) in order to evaluate the functionality in the activities of daily living, therefore the participant's autonomy level.

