2.5 Time schedule

All individuals with numbers 1-146 (groups A to C) will undergo the main evaluations, assessments and interventions and a blood sampling in the beginning of the study. Differences among groups concern the timing and the frequency of these interventions (figure 1). The last 25 participants (control group) will not test the FrailSafe system, but will receive two clinical evaluations, one blood taking and one telephone follow up interview. For all participants, data regarding social interaction and natural language analysis will be collected by their entry to the study. Data collection of written text will be repeated in the context of each clinical evaluation session.

[figure not shown]

Figure 1. FrailSafe study's time schedule per group and per center

In each clinical center the procedures followed are:

Eighty participants of group A were supposed to undergo a clinical evaluation, a blood sampling and a FrailSafe system instauration at the time of their recruitment (\geq M6). However, the FrailSafe home visit, along with the blood drawing which accompanies it, was not possible to be done on time for all participants of group A. The reasons for this, along with a proposed mitigation strategy are described below (section 2.6). The second clinical evaluation session and FrailSafe system utilization is scheduled for M26 and a last clinical evaluation will take place in M33. Meanwhile, in 3 months intervals, there is the telephone follow up questionnaire up until M36, unless it coincides with a clinical evaluation or a FrailSafe home visit session, where it will be administered in person and not by telephone. A second blood sampling will take place in M27 only for a subgroup of participants in the clinical center of Patras' University.

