The participants of group B (40 subjects) started in M10 by the clinical evaluation session. Similarly as in group A, and mainly because of the delay in this first group, the first FrailSafe system installation for group B, along with the blood taking that accompanies it, is not yet completed. The proposed mitigation strategy is described below (section 2.6). In this group the FrailSafe system application will be more intensive, every two or three (only for the first sessions) months, from M12 to M27, for a total of 7 times. The second and third clinical evaluation sessions will take place in M16 and M22 respectively. Finally, a last clinical evaluation session with take place in M35. Telephone follow up assessments will be done every 3 months' time from M26 to M36, but the follow up questionnaire will be administered in person in every FrailSafe home visit also from M12 to M22, during the corresponding appointments. In practice, group B due to its frequent FrailSafe home visits will receive no more than 2 follow up phone calls (M29 and M32). A second blood sampling will take place in M25 only for a subgroup of participants in the clinical center of Patras' University.

The group C will be the group to test the FrailSafe system in its integrity as it will be developed by the interactions and adaptations from the previous groups' experience. Starting in M31 the triplet clinical evaluation, blood sampling and FrailSafe system will be applied. Twenty of the participants in this group will have the FrailSafe system for 5 days (as used by the other groups also), 3 times in total with 2 months' intervals (M31 to M35). On the other hand, five individuals of group C will be asked to carry the FrailSafe system for 60 days in continuation. At the end of the FrailSafe system testing, a satisfaction interview will be conducted to each group C individual. All group C participants will receive a second clinical evaluation in the end of the study (M36) and a follow up questionnaire in M33 for the first arm of group C in M34 by telephone call. A second blood sampling will take place in M35 only for a subgroup of participants in the clinical center of Patras' University.

Finally the group D (control group) will receive no application of the FrailSafe system. A blood sampling will take place in the recruitment (M31), together with a clinical evaluation

session. The latter will be repeated once more at the end (M36). One telephone follow up will take place in M33.

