2.6 Deviations from the original plan and proposed mitigation actions

Already since the beginning of the study, due to delays in obtaining the Ethical Committees' approval in Nancy (France) and to limited availability of the FrailSafe system devices, there was a certain delay that affected the starting of mainly group A and partially of group B.

We have elaborated a proposed mitigation plan of a modified timetable for FrailSafe home visits in order to catch up with "lost" FS evaluations in group A, schematically depicted as following:

M 11	M		M 14	M 15	M 16	M 17	M 18	M 19	M 20	M 21	M 22	M 23	M 24	M 25	M 26	M 27	M 28	M 29	M 30	M 31	M 32	M 33	M 34	M 35	M 36
A1 a		B1	A1 b		32	A1 c		3	_	4		5		36		57		A2					up C		
Le	ege	nd:																							
А	1a			M1	.1						firs	t cyc	le fir	rst pa	rt 1-	-27(c	one r	nont	th)						
A	1b			M1	.4						firs	t cyc	le se	econc	l par	t 28-	·52(c	one r	nont	th)					
A	1c			M1	.7						firs	t cyc	le th	ird p	art 5	53-80)(one	e mo	onth)						
A	2			M2	8-30)					sec	ond	cycle	e 1-8	0 (th	ree I	mon	ths)							
В	1			M1	2-13	3					firs	t cyc	le 81	1-120)										
В	2			M1	.5-16	5					sec	ond	cycle	e 81-	120										
В	3			M1	8-19)					thir	d cy	cle 8	31-12	0										
B	4			M2	20-21	L					fort	h cy	cle 8	31-12	0										
В	5			M2	2-23	3					fiftl	п сус	le 8	1-120)										
В	6			M2	4-25	5						•		1-12											
В	7			M2	26-27	,					sev	enth	сус	le 81	-120	1									

Figure 2. Mitigation action proposed for the FrailSafe system sessions

More analytically the plan proposes:

- The split in three of group A's first cycle of FrailSafe session and its interference between the 1st-3rd sessions of group B (M11,M14, M17)
- The decrease of the duration of FS session for group A (3-5 days instead of 5)*
- The reduction for group B of the total number of FrailSafe sessions' cycles in 7 (instead of 9 initially scheduled)
- No change in the conduction of the study for groups C and D (M31 and after).

*this proposal about the duration derives from the need to do all 80 first FrailSafe sessions per center in the shortest delay possible in order not to disturb too much the continuation of the study with the recruitment of group B. Taking into account that no more than five FrailSafe sessions can run simultaneously because of material and personnel availability reasons, the shortest time frame possible to make 80 FrailSafe home sessions is almost 3 months, as illustrated in the following schema:

H2020-PHC-690140-FRAILSAFE

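### For group A, the start rules for the hard-outcome questionnaire (Table 17) contradict each other once the first home visits move to M11, M14 and M17

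*Protocol*

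**What the plan says.** Months are project months (M).

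- **Section 3.3, trigger and interval.** The trigger is "After the first evaluation triplet takes place (clinical assessment appointment, FrailSafe system home visit and blood sampling), the follow up"; the interval is given as "This follow up, which is programmed for every 3 months' time, will be done either by telephone" or at a coinciding visit. Table 17 collects dated falls, fractures, hospitalisations and deaths, and separates planned from urgent admissions. It states no recall window. The same section calls these events the study's hard outcomes.
- **Section 4.2 step 12, group A.** "Telephone Follow-up after the retrieval of the FrailSafe in a 3 months' basis (table 17). (M9-M24". One line therefore carries both a trigger (device retrieval) and a calendar.
- **Section 2.5.** Group A was meant to have "a FrailSafe system instauration at the time of their recruitment" (M6 or later), but the home visit with its blood draw "was not possible to be done on time for all participants of group A". The section then says "Meanwhile, in 3 months intervals, there is the telephone follow up questionnaire up until M36", without naming a trigger.
- **Section 2.6.** The mitigation is "The split in three of group A's first cycle of FrailSafe session and its interference between the 1st-3rd sessions of group B (M11,M14, M17". The legend to Figure 2 assigns numbers 1-27, 28-52 and 53-80 in each centre to these three months.
- **Where Table 17 is asked.** Section 4.2 step 8 (first home visit) does not list it, while step 15 (second home visit) does. Annex 19 lists it among installation-visit tasks without limiting it to later visits.

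**The concern.** The trigger and the M9 start agree only under the original timetable, with the home visit at M6 and the first call three months later. Section 2.6 moved the home visit, and neither start rule was revised. Three centres could each follow the text and begin collecting hard outcomes in different months.

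On the literal trigger, the start of dated outcome collection would depend on the ID block, and a participant would have to remain in the study until the home visit before being asked. Section 2.5 replaces people who leave early, including by death, so early events could drop out of the followed cohort. ADL/IADL decline is also a hard outcome (section 5.2.1), and its six-monthly assessment is attached to the same questionnaire (section 3.3), so its schedule is equally unclear.

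Section 5.2.2 plans a survival analysis of hard outcomes, for example a Cox model, after group A's second clinical evaluation. That is the group affected. The protocol itself expects few hard outcomes, so missed or misdated early ones would matter.

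**Working it through.** **Inputs.** First home session by ID block: M11 (1-27, n = 27), M14 (28-52, n = 25), M17 (53-80, n = 28), from section 2.6; 27 + 25 + 28 = 80 per centre. Call interval: 3 months (section 3.3). Entry month: M6 or later (section 2.5); actual months are not given. As a range I take M6 as the early end. I take M10 as an assumed late end, because of group B section 2.5 says "The participants of group B (40 subjects) started in M10 by the clinical evaluation session".

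**1. The protocol's own date.** Home visit M6 + 3 = M9. The start in section 4.2 step 12 is reproduced under the original plan.

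**2. The same rule under section 2.6.** 11 + 3 = M14; 14 + 3 = M17; 17 + 3 = M20. M9 is not reproduced; it precedes every mitigated session.

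**3. Wait from entry to home visit (home-visit month minus entry month), trigger read literally.**

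| Assumed entry | 1-27 | 28-52 | 53-80 | Weighted mean |
|---|---|---|---|---|
| M6 | 5 | 8 | 11 | (27×5 + 25×8 + 28×11)/80 = 643/80 = 8.0 |
| M10 | 1 | 4 | 7 | (27×1 + 25×4 + 28×7)/80 = 323/80 = 4.0 |

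The means treat everyone in a block as having waited for the mitigated month. If Table 17 is asked at installation, as Annex 19 suggests, these are the waits to first questioning. If it is first asked three months after the session, add 3: 8, 11 and 14 months (mean 11.0) from M6, or 4, 7 and 10 (mean 7.0) from M10.

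**4. The calendar read literally.** Calls fall at M9, M12, M15, M18, M21 and M24. Before the mitigated session, block 1-27 has one call (M9), block 28-52 has two (M9, M12) and block 53-80 has three (M9, M12, M15). With entry at M6 no interval exceeds 3 months.

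**5. Can the clinical evaluation fill the gap?** The second evaluation is at M26 (section 2.5) or M27 (section 4.2 step 13). Table 6 asks about falls in the last year, which reaches back to 26 - 12 = M14 or 27 - 12 = M15. Hospitalisations and fractures are asked over three years, which reaches past M6 but also to before the study, so events before and after entry are mixed. All three are counts. The only timing item concerns the last fracture and is expressed as months before the study. Planned and unplanned admissions are not separated, whereas section 5.2.1 counts only unplanned ones. Table 6 therefore cannot supply dated hard outcomes.

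**The case against.** The strongest reply is that this is a scheduling inconsistency and not a demonstrated loss of data. Much of that stands.

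- **The calendar.** A reader might infer that follow-up starts only after the home visit. The documents do not settle that: step 12 also prints M9 to M24, and section 2.5, which reports the delay, keeps three-monthly calls with no device trigger.
- **Not asked is not lost.** Table 17 takes dates and has no recall limit, and Annex 19 places it at installation. A first questionnaire could reach back to entry, although nothing says it must.
- **Table 6.** A reader might infer that nothing before about M14 is covered. That is true of falls only; the three-year items reach further, though without usable dates.
- **Deaths and exits.** Table 20 records death, withdrawal and loss to follow-up at any time, and the serious adverse event form in Annex 20 records hospitalisation and dated death. Table 17 is not the sole record.
- **Extent.** Multiplying the mean wait by all 240 group A participants is tempting but unsupported. Section 2.5 says only that not every visit was on time, and section 3.7.8 shows that some early sessions took place in Patras and Cyprus.
- **Device analyses.** The Technical and Combined Frailty Indices do not exist before the first session (section 5.1), so earlier events could not serve as prospective outcomes for them. The exposure lies in analyses based on clinical predictors and in the event record.
- **Group B.** Section 2.5 has Table 17 asked in person from M12 after clinical evaluation at M10, so no comparable gap is shown.
- **Time origin.** This may properly be left to a statistical analysis plan. But the plan cannot supply coverage dates that the collection rules do not require anyone to record.

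**Conclusion.** The contradiction stands: for group A participants whose first session was delayed, the triplet or retrieval trigger, the M9 to M24 dates and the M11/M14/M17 sessions are incompatible, and the text does not say which governs. Its consequence ranges from almost nothing, if centres used the calendar, to the waits in step 3 of the working, if they used the trigger. Those waits rest on assumed entry months and apply only to people actually delayed, whose number is not given. Data loss is possible but not established, and no participant-month total should be quoted. The existing back-ups soften the problem without resolving it, because none is required to give dated, unplanned-only hard outcomes from entry. The matter should be corrected before the survival analysis that follows group A's second evaluation.

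**What to change.** 1. Reconcile sections 3.3, 4.2 step 12 and 2.6 by tying the three-monthly Table 17 schedule to the first clinical evaluation, whether or not the home visit has taken place. Group B needs only the same wording.
2. This revision was written at M23, so the new rule comes too late for most of group A's early period. For group A participants who were not asked on the M9 calendar, administer Table 17 once at the M26-M27 contact for the whole period since entry, with event dates, and flag those events as back-filled.
3. Record for each person the date from which hard outcomes are actually covered, and start at-risk time there in the hard-outcome survival analysis. Count deaths and exits before the home visit from Table 20 and the serious adverse event forms.
4. Align section 4.2 step 8 with Annex 19 on whether Table 17 is asked at the first home visit, and state its recall window.

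The cost is a few wording changes and one extra set of questions at a contact already scheduled. The drawback is longer recall for back-filled events, which is why they need a flag. Past ADL/IADL scores cannot be recovered this way, since those scales describe current function.
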